6.4 TREATMENT

6.4.1 Acute treatment

Patients will be randomized to one of the following treatment groups:

Group I	Catheter-directed thrombolytic therapy with rt-PA in addition to conventional treatment with low molecular weight heparin (for details – see 6.4.2)
Group II	Conventional treatment with low molecular weight heparin (see 6.4.3)

Drugs will be ordered from the hospital's pharmacy according to local routines.

- Group I will be given rt-PA (Actilyse®) combined with unfractionated heparin and followed by low molecular weight heparin (LMWH) and warfarin.
- Group II, the conventional treatment arm, will be given LMWH, either sc dalteparin (Fragmin®), 200 IU/kg od, or enoxaparin (Klexane®), 1.5 mg/kg od, according to local routines, and warfarin.

6.4.2 Group I - Catheter-Directed Thrombolytic (CDT) therapy – procedures

- **Anticoagulant and fibrinolytic therapy**

- Discontinue oral anticoagulants - INR should be <1.5 before the procedure.
- In case of prior sc LMWH therapy treatment should be discontinued at least 8 h before the procedure, and in case of prior UFH treatment APTT (Cephotest®) should be adjusted to 40-60 sec during the procedure (see below).
- An iv bolus dose of UFH, 5000 U, should be given followed by continuous iv UFH¹ infusion at 15 U/kg/h. Adjust dose to keep APTT (Cephotest®) at 40-60 sec, first adjustment 6-12 h after start of treatment.
- During the thrombolytic treatment keep APTT (Cephotest®) at 40-60 sec.
- At the completion of thrombolytic treatment:
 - ✓ discontinue UFH
 - ✓ give sc LMWH after 1 h, (either dalteparin, Fragmin®, 200 U/kg bid, or enoxaparin, Klexane®, 1,5 mg/kg bid).
 - ✓ Oral warfarin (Marevan®) will be initiated according to local routines.
 - ✓ LMWH will be discontinued when INR has been in therapeutic range (2.0-3.0) for at least 24 hours, but should not be given for less than total 4-5 days.

- **Interventional procedures.** In an interventional radiology unit, an introducer will be inserted into an appropriate vein, preferentially the popliteal vein, guided by ultrasound to prevent puncture of the artery or laceration of the vein wall and to secure only a single puncture. If possible, the wire and catheter should be introduced above the proximal part of the thrombus (use fitting-sized perfusion catheters, e.g., 10, 20, 30, or 50 cm). A venography should then be performed to disclose the topography of the thrombus. CDT may be discontinued if introduction of the catheter through the occluded segment is not successful. Catheters should be properly fixed to the skin.

The perfusion catheter (and the perfusion wire) should cover the central to peripheral part of the thrombus. Rt-PA (Actilyse®), 20 mg diluted in 500 ml 0.9% NaCl, will be infused at 0.01 mg/kg/h. Maximal dose infused will be 20 mg/24 h. The rt-PA dosage may be split into two catheters using lower concentration, keeping flow the same.

¹ A suitable working solution should be made to contain UFH 40 U/ml in 0.9% NaCl, e.g., mix 20000 U of UFH in 500 ml 0.9% NaCl or 40000 U in 1000 ml 0.9% NaCl. The infusion rate (ml/h) then reflects total units of UFH per 24 hrs in thousands, e.g., 25 ml/h corresponds to 25000 U/24 h, 30 ml/h 30000 U/24 h, and so on.

After insertion of catheter, venography, and start of iv UFH and iv rt-PA infusion, treatment will continue in medical wards. Blood pressure and pulse and the puncture site are assessed 4 times a day. Hemostasis is also monitored by daily analysis of hemoglobin, fibrinogen, D-dimer, INR, and platelet counts. APTT is monitored twice daily for adjustment of heparin dose. The patient will be encouraged to use the muscle pump of the leg while in bed. No food and drink restrictions.

Effect of treatment will be assessed by venography at least every 24 hrs, and catheters repositioned accordingly. Treatment should normally not continue for >96 h. At the end of treatment, the catheters will be removed immediately and hemostasis obtained by manual compression of the puncture site. Pressure will be continued for 2 hrs with a roll while the patient is immobilized.

- **Stents.** Balloon dilatation and placement of venous stents will be performed at the discretion of the operator to establish flow and to obtain <50% residual stenosis.
- **Concomitant medication during procedure.** During the interventional procedure concomitant use of other antithrombotic agents should be avoided because of increased risk of bleeding. This includes antiplatelet agents (e.g., acetylsalicylic acid, thienopyridines, GPIIb/IIIa inhibitors, non steroidal anti-inflammatory agents, or other) or anticoagulants (e.g., low molecular weight heparin, pentasaccharide, warfarin, or other). Concomitant use of ACE-inhibitors appears to increase the risk of anafylactoid reactions.

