1 SYNOPSIS

Deep vein thrombosis (DVT) is a severe disease which may cause severe disability and which is sometimes fatal. Conventional treatment with low molecular weight heparin (LMWH) and oral anticoagulants is associated with some degree of long-term sequelae, i.e., post-thrombotic syndrome (PTS), in more than 60-80% of the patients. Systemic thrombolytic therapy reduces the risk of PTS, but is associated with an unacceptably high risk of bleeding complications, many being disabling or fatal. Catheter-directed thrombolytic (CDT) therapy is a novel treatment modality which has been introduced in many hospitals worldwide. Low dose fibrinolytic agents are delivered continuously and directly into the thrombus through a catheter until thrombus has dissolved. Although many, mostly small series, have suggested a beneficial effect of this costly treatment in terms of increased patency of the veins and improved short term functional outcome, there are no randomized clinical trials documenting its short and long-term efficacy and safety.

The present study is a randomized, open-label, multi-center clinical trial among hospitals in the Eastern and Southern Norway Health Authorities (Helse Øst and Sør). Patients with acute iliofemoral vein thrombosis will be randomized to either conventional treatment or CDT in addition to conventional treatment. Main outcome parameters are patency rates at 6 months and prevalence of PTS at 24 months. A number of secondary outcomes include bleeding complications, recurrent thrombosis, quality of life (QoL), markers of importance for successful lysis and recurrent thrombosis, and whether PTS is related to patency at the end of treatment.

Our main short-term hypothesis is that CDT of first-time acute DVT will increase patency of the affected iliofemoral vein segments after 6 months from <50% on conventional therapy to >80% after CDT. Our main long-term hypothesis is that CDT will improve long-term functional outcome, i.e., risk of PTS, assessed after 2 years, from >25% on conventional treatment to <10% after CDT. The estimated sample size is at least 100 evaluable patients in each group using a statistical significance (α) = 5% and a statistical power ($1-\beta$) = 80%.

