3.2 SECONDARY OBJECTIVES

- 3.2.1 To investigate frequency of clinically relevant bleeding related to the procedure.
- 3.2.2 To investigate effects on quality of life (QoL).
- 3.2.3 To investigate cost-effectiveness of treatment.
- 3.2.4 To investigate the procedural success of CDT.
- 3.2.5 To identify markers of importance for successful thrombolysis.
- 3.2.6 To investigate patency at 2 years.
- 3.2.7 To investigate PTS at 6 and 60 months.
- 3.2.8 To investigate whether presence or absence of PTS at any time point is related to patency at end of treatment.
- 3.2.9 To investigate prevalence of vein anomalies (and need for angioplasty or stents).
- 3.2.10 To investigate prevalence of underlying thrombophilia.
- 3.2.11 To investigate frequency of recurrent VTE during follow-up.
- 3.2.12 To identify markers of importance for recurrent thrombosis.

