6.4.3 Group II – conventional treatment with LMWH

Patients allocated the conventional treatment arm will be given sc LMWH, either dalteparin (Fragmin®), 200 U/kg od, or enoxaparin (Klexane®), 1.5 mg/kg od, according to local hospital routines, and simultaneous warfarin (Marevan®) according to local routines. LMWH will be discontinued when INR has been in therapeutic range (2.0-3.0) for at least 24 hours, but should not be given for less than total 4-5 days.

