8.2 Statistical methods

All statistical analysis will be performed according to the intention-to-treat principle. If ineligible patients are mistakenly included, they may be excluded (ref Ferguson et al BMJ 2002), apart from this, no other post-randomization exclusions will be made. The effect of treatment will be determined using 2x2 tables with assessment of the difference between patent vessels and prevalence of PTS, relative risks, and odds ratios with 95% confidence limits. The prevalence of clinically relevant bleeding, PTS, vein anomalies, thrombophilia, recurrent DVT will be determined using point estimates with 95% confidence intervals. A stratification analysis will be carried out using the Mantel-Haenzel method. Differences in baseline characteristics may be adjusted for using a multivariate logistic model. This may be done if there are substantial differences between the two groups, and if the variable(s) is probably or certainly associated with the outcome measure, e.g., age and previous VTE. Missing data on end-point variables will be scored as previous score or last/worst score carried forward.

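### Protocol 6.4.2 orders LMWH twice daily for Group I after lysis, at twice the daily dose of the conventional regimen that Group I is defined to receive

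*Protocol*

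**What the plan says.** **Definition of the arms.** In the synopsis, patients "will be randomized to either conventional treatment or CDT in addition to conventional treatment". Section 6.4.1 defines Group I as "Catheter-directed thrombolytic therapy with rt-PA in addition to conventional treatment with low molecular weight heparin" and points to 6.4.2 for the details.

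**Conventional LMWH.** The regimen is stated twice, for Group II, and both statements are once daily. Section 6.4.1 gives dalteparin "200 IU/kg od, or enoxaparin (Klexane®), 1.5 mg/kg od, according to local routines". Section 6.4.3 gives dalteparin "200 U/kg od, or enoxaparin (Klexane®), 1.5 mg/kg od, according to local hospital routines".

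**LMWH in Group I.** Section 6.4.2 stops UFH when lysis is complete and starts subcutaneous LMWH 1 h later: "either dalteparin, Fragmin®, 200 U/kg bid, or enoxaparin, Klexane®, 1,5 mg/kg bid". No other place in the protocol gives a frequency for Group I.

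**Stopping rule.** Section 6.4.2 says that "LMWH will be discontinued when INR has been in therapeutic range (2.0-3.0) for at least 24 hours", with a minimum total of 4-5 days. Section 6.4.3 gives Group II the same rule in the same words.

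**The concern.** If Group I is CDT plus conventional treatment, its LMWH after lysis should be the conventional regimen. The dosing line in 6.4.2 names the same two drugs at the same doses per kg but doubles the number of injections per day. The protocol gives no reason for a stronger regimen in this arm.

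Two things are at stake.

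- **Patient safety.** The line is an operative instruction for patients who have just received rt-PA and had a catheter removed from a punctured vein. The protocol is cautious about anticoagulation up to that point: it sets an APTT target during the infusion and tells centres to avoid other antithrombotic agents because of bleeding. The registry cited in section 2 reports major bleeding in 11% of CDT patients, 39% of it at the insertion site. An unexplained doubling of LMWH straight afterwards does not fit that approach.
- **Interpretation of bleeding.** Objective 3.2.1 is "To investigate frequency of clinically relevant bleeding related to the procedure", and section 8.2 states: "The prevalence of clinically relevant bleeding, PTS, vein anomalies, thrombophilia, recurrent DVT will be determined using point estimates with 95% confidence intervals". If centres follow the line, bleeding after lysis in Group I could partly reflect doubled LMWH rather than CDT plus conventional treatment.

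**Working it through.** **Comparison of the two regimens**

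| Element | Group I after lysis (6.4.2) | Conventional (6.4.1, 6.4.3) |
|---|---|---|
| Dalteparin per injection | 200 U/kg | 200 U/kg |
| Enoxaparin per injection | 1.5 mg/kg | 1.5 mg/kg |
| Frequency | *bid* | *od* |
| Stopping rule | INR 2.0-3.0 for at least 24 h, minimum total 4-5 days | same |

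In drug, dose per kg and stopping rule the regimens match. In the LMWH dose they differ only in frequency.

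**Daily dose** = dose per injection × injections per day.

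- Dalteparin: 200 × 2 = 400 U/kg per day, against 200 × 1 = 200. Ratio 400 / 200 = 2.0.
- Enoxaparin: 1.5 × 2 = 3.0 mg/kg per day, against 1.5 × 1 = 1.5. Ratio 3.0 / 1.5 = 2.0.

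**Excess per day** = 400 − 200 = 200 U/kg, or 3.0 − 1.5 = 1.5 mg/kg. Body weight is not given, so the weights below are assumptions:

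| Assumed weight | Dalteparin excess per day | Enoxaparin excess per day |
|---|---|---|
| 60 kg | 200 × 60 = 12,000 U | 1.5 × 60 = 90 mg |
| 75 kg | 200 × 75 = 15,000 U | 1.5 × 75 = 112.5 mg |
| 100 kg | 200 × 100 = 20,000 U | 1.5 × 100 = 150 mg |

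**When the excess starts.** The first injection, 1 h after UFH stops, is the same under either reading. With an assumed 12 h spacing, the second falls at 1 + 12 = 13 h, against 1 + 24 = 25 h once daily. The excess therefore begins about 13 h after UFH stops.

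**How long it lasts.** It runs until the INR, which should be below 1.5 before the procedure, has been at 2.0-3.0 for at least 24 h. No upper limit is stated. The 4-5 day minimum allows an illustration. If that many full days of LMWH fell after lysis, the excess would be 200 × 4 = 800 to 200 × 5 = 1,000 U/kg of dalteparin, or 1.5 × 4 = 6 to 1.5 × 5 = 7.5 mg/kg of enoxaparin. This is not a firm lower bound, because the minimum is a total and may include LMWH given before the procedure.

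**Twice-daily dose with the conventional daily total.** 200 / 2 = 100 U/kg of dalteparin, or 1.5 / 2 = 0.75 mg/kg of enoxaparin, per injection. Any larger twice-daily dose exceeds the conventional total.

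**Patients affected.** Group I patients who complete lysis: at most about 100, from the approximately 100 per group in section 8.1.

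**The case against.** The strongest counter-argument is that there is no strict contradiction. The *od* doses are written only for Group II. The definition of Group I refers the reader to 6.4.2, so that section governs. Section 8.1 also uses conventional treatment in a broad sense: heparin or LMWH followed by oral anticoagulants. On that reading, twice-daily LMWH plus warfarin is still conventional treatment, and the fault is only an unexplained difference between the arms.

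This is a fair reading of the cross-reference, but it does not rescue the line. A deliberately different regimen would be expected to show some adjustment or reason. Instead the drugs, the doses per kg and the stopping rule are all carried over, and only the frequency changes. If the difference was nevertheless intended, the synopsis and 6.4.1 describe Group I inadequately. The text needs correction in either case.

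Other points stand as limits:

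- The protocol favours *od* but does not prove it. The dose per injection of an intended twice-daily regimen could be the error instead.
- Harm is not demonstrated. The protocol does not show what centres gave. Daily haemoglobin, platelets, APTT and INR in hospital, and the exclusions for bleeding diathesis, thrombocytopenia and severe renal failure, may help to limit or detect harm. They do not correct the dose.
- Objective 3.2.1 covers bleeding related to the procedure. The protocol does not say whether a bleed on LMWH more than half a day after lysis would count, so the effect on that estimate is possible rather than certain.

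**Conclusion.** The concern holds. As written, section 6.4.2 gives Group I exactly twice the conventional daily LMWH dose from the second injection onward, and nothing in the protocol explains or corrects this. The factor of 2 depends on no assumption. The absolute excess (12,000-20,000 U of dalteparin or 90-150 mg of enoxaparin per day) assumes a body weight of 60-100 kg, and the start at about 13 h assumes 12 h spacing.

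The point must be fixed because a dosing instruction after thrombolysis conflicts with the definition of the arm, not because a bias in a result has been shown. Bleeding during the infusion is unaffected, and no effect on 6-month patency, 2-year PTS or the sample size is claimed. Confidence is high that the discrepancy exists. That once daily was intended is only the likelier reading.

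**What to change.** 1. Have the clinical leads confirm the intended regimen in 6.4.2.
2. If the conventional regimen was intended, change *bid* to *od* for both drugs, so that the line reads dalteparin 200 U/kg *od* or enoxaparin 1.5 mg/kg *od*, in agreement with 6.4.1 and 6.4.3. The daily dose ratio between the arms then becomes 1.0.
3. If a twice-daily regimen was intended, state its correct dose per injection. If its daily total differs from the conventional one, describe Group I in the synopsis and 6.4.1 as CDT plus that regimen, so that bleeding results are read accordingly.
4. In either case, promptly notify the four CDT centres listed in section 11.1 and the ethics committee.

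The cost is one clinical confirmation, two words in one line under the likelier reading, and the notices. Sample size, visits and analyses do not change.

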6.4.3 Group II – conventional treatment with LMWH

Patients allocated the conventional treatment arm will be given sc LMWH, either dalteparin (Fragmin®), 200 U/kg od, or enoxaparin (Klexane®), 1.5 mg/kg od, according to local hospital routines, and simultaneous warfarin (Marevan®) according to local routines. LMWH will be discontinued when INR has been in therapeutic range (2.0-3.0) for at least 24 hours, but should not be given for less than total 4-5 days.

6.4.4 Subacute and chronic phase after DVT

Patients will be treated with warfarin for at least 6 months with target INR 2.0-3.0. All patients will be advised to use knee-high compression stockings, grade II, for 6 months.

6.5 VISITS AND PROCEDURES DURING FOLLOW-UP

End-point assessment will be performed by a vascular surgeon with no previous contact or knowledge of patients' medical history or treatment allocation. At each visit the patients will explicitly be told not to reveal treatment allocation.

6.5.1 Visit 1 (trial entry – at hospital admission/)

- 6.5.1.1 Case history and general clinical examination.
- 6.5.1.2 Compression ultrasonography or venography, alternatively CT or MRI angiography diagnosing acute iliofemoral DVT.
- 6.5.1.3 Laboratory screening (hemoglobin, platelets, leukocytes, creatinine, ASAT, ALAT, GT, bilirubin, INR, APTT, D-Dimer, cholesterol, and CRP).
- 6.5.1.4 Thrombophilia screening (collection of blood samples).
- 6.5.1.5 Assessment of baseline QoL before treatment using VEINES-QoL and EQ-D5 (Appendix 2).
- 6.5.1.6 Assessment of baseline clinical score using Villalta^{5:43} score and the C classification of CEAP, see Definitions.

6.5.2 Visit 2 (hospital stay)

- 6.5.2.1 Daily assessment of hemoglobin, platelets, fibrinogen, APTT, INR, and D-Dimer, and bilateral leg circumference.
- 6.5.2.2 Daily venography will be performed in patients allocated CDT.
- 6.5.2.4 Bleeding complications.

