6.5.3 Visit 3 – 6 m ± 2 weeks

- 6.5.3.1 Clinical history – recurrent thrombosis – malignancy.
- 6.5.3.2 Clinical PTS scores according to Villalta and CEAP. Bilateral leg circumference.
- 6.5.3.3 Assessment of functional venous obstruction by air-plethysmography.
- 6.5.3.4 Ultrasonographic assessment of postthrombotic changes, patency, and reflux⁴⁴⁻⁴⁷.
- 6.5.3.5 Quality of Life (QoL) assessment (Appendix 2).
- 6.5.3.6 D-dimer testing, INR, thrombophilia screening (if previously inconclusive).

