6.5.4 VISIT 4 – 12 m ± 4 weeks

Telephone interview – recurrent thrombosis – malignancy.

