6.5.5 VISIT 5 – 24 m ± 4 weeks

- 6.5.5.1 Clinical history – recurrent thrombosis – malignancy.
- 6.5.5.2 Clinical PTS scores according to Villalta and CEAP. Bilateral leg circumference..
- 6.5.5.3 Assessment of functional venous obstruction by air-plethysmography.
- 6.5.5.4 Ultrasonographic assessment of postthrombotic changes, patency, and reflux
- 6.5.5.5 Quality of Life (QoL) assessment (Appendix 2).
- 6.5.5.6 D-dimer, INR, thrombophilia screening (if previously inconclusive).

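### Bleeding has no scheduled collection after the hospital stay and no time window common to both arms, although the protocol promises a safety comparison

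*Protocol*

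**What the plan says.** **Outcome and objective.** The Synopsis states: "A number of secondary outcomes include bleeding complications". Secondary objective 3.2.1 is narrower: "To investigate frequency of clinically relevant bleeding related to the procedure". Section 6.1 describes a randomised study of both effect and safety against conventional therapy. Section 7.4 defines major, clinically relevant non-major and trivial bleeding without reference to arm, procedure or time. Section 8.2 plans point estimates with 95% confidence intervals for clinically relevant bleeding and gives no window.

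**Collection.** Under Visit 2 (hospital stay) the schedule has "6.5.2.4 Bleeding complications". It applies to both arms, as does daily haemoglobin. At 6 months the history item is "6.5.3.1 Clinical history – recurrent thrombosis – malignancy", at 12 months "Telephone interview – recurrent thrombosis – malignancy", and at 24 months "6.5.5.1 Clinical history – recurrent thrombosis – malignancy". The 36-month and 60-month contacts name the same two events, and the 48-month call adds PTS screening. Bleeding is named at none of them.

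**Exposure.** Section 6.4.4 applies to both arms: "Patients will be treated with warfarin for at least 6 months".

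**The concern.** Bleeding is the main harm to be weighed against any reduction in PTS. The Background (section 2) cites 11% major bleeding in a CDT registry. A fair comparison needs the same outcome, counted over the same period, in both arms. The protocol fixes neither. The objective ties bleeding to a procedure that only one arm undergoes, and the only scheduled collection ends at a discharge date that is not defined and may come at different times in the two arms. Bleeding on warfarin after discharge, a risk in both arms, has no planned place in the data. Later analysis planning could not repair this, because it cannot recover events that were never recorded.

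**Working it through.** The protocol gives no bleeding rate, power or window for this comparison, so there is no stated figure to reproduce. The check is mainly textual, with arithmetic for scale.

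**1. Visit schedule (6.5.1 to 6.5.8).** Bleeding appears at Visit 2 and at none of Visits 3 to 8. Recurrent thrombosis and malignancy appear at every one of those six contacts. The addition of PTS screening at Visit 7 shows that the lists were written contact by contact.

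**2. Objective against the other sections.** Read literally, 3.2.1 gives the conventional arm zero events by definition. That does not fit a between-arm safety aim (6.1), arm-neutral definitions (7.4) or an estimate of clinically relevant bleeding in general (8.2).

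**3. Length of stay.** No section gives it for either arm. In the CDT arm, lysis normally lasts up to 96 h, and warfarin starts when lysis ends (6.4.2). In the conventional arm, LMWH and warfarin start together (6.4.3). Both arms have the same minimum of 4-5 days of LMWH in total. A longer CDT stay is therefore likely, but it is an inference: discharge is not tied to the end of LMWH.

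**4. Share of the warfarin period covered.** Taking 6 months as 182.5 days and assuming the stay:

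| Assumed stay (days) | Stay / 182.5 |
|---|---|
| 1 | 0.5% |
| 5 | 2.7% |
| 9 | 4.9% |
| 14 | 7.7% |

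These are shares of time, not of bleeds. If the hazard were constant and the 6-month risk 2% to 10%, stays of 1 to 9 days would miss about 95% to 99% of bleeds. Early clustering would lower that share.

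**5. What window length alone could do.** Assume the same constant hazard in both arms. With 6-month risk R, the daily hazard is λ = −ln(1 − R)/182.5 and the share observed in d days is 1 − exp(−λd). For R = 5%, λ = 0.0513/182.5 = 0.000281:

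| Conventional vs CDT (days) | Observed | Ratio, CDT / conventional |
|---|---|---|
| 5 vs 5 | 0.14% vs 0.14% | 1.0 |
| 5 vs 7.2 | 0.14% vs 0.20% | 1.4 |
| 5 vs 9 | 0.14% vs 0.25% | 1.8 |
| 3 vs 9 | 0.08% vs 0.25% | 3.0 |
| 1 vs 9 | 0.03% vs 0.25% | 9.0 |

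The 9 days combine the 96 h ceiling (4 days) with 5 days of bridging. The 7.2 days use the registry's mean infusion of 53 h from the Background: 53/24 = 2.2, plus 5.

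The absolute difference depends on the hazard. With a daily risk h in hospital and 1 − (1 − h)^d, 9 vs 5 days gives 1.8% vs 1.0% at h = 0.2%, 4.4% vs 2.5% at 0.5%, and 8.6% vs 4.9% at 1%. At 0.5%, 7.2 vs 5 days gives 3.5% vs 2.5%. For the 9 vs 5 day pairing alone, the artefact runs from 0.25 − 0.14, about 0.1 percentage points, to about 3.7 (8.65 − 4.90). Neither hazards nor stays come from the protocol, so these figures show the mechanism and do not estimate a bias.

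**The case against.** The strongest reply is that this is a deliberate, procedure-focused safety outcome. Objective 3.2.1 asks about procedural bleeding, the CDT hospital stay is where most of it would be seen, and Visit 2 records it with daily haemoglobin. In section 8.2 the treatment-effect tables name patency and PTS, while bleeding is to be estimated with an interval. This stands as far as it goes: procedural risk in the CDT arm can be described from the data as planned. It does not supply the safety comparison that 6.1 promises.

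It may also be said that the clinical history at Visits 3, 5 and 8 would bring bleeds to light. Some, perhaps, but the item names two other events, and unprompted reporting is not systematic. Section 7.4.2 mentions a safety monitoring committee, and pages between sections 11.1 and 12 were not available, so a reporting route outside the visit schedule cannot be excluded. The visit schedule itself is fully visible.

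A reader might go further and infer that the arms are observed over unequal windows and that the comparison is therefore biased against CDT. The protocol does not support that. It states no length of stay, and with equal stays the window effect disappears. Pairing 9 with 5 days sets the ceiling for lysis against minimum bridging. Bleeding during lysis is also a genuine risk of the allocated treatment, not an artefact of longer observation.

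**Conclusion.** The point holds as a gap in collection and an inconsistency of definition. Three things rest on the text alone: bleeding is a scheduled item only during a hospital stay of undefined length; objective 3.2.1 has no counterpart in the conventional arm, although 6.1 promises a comparison; and no later contact names bleeding, although both arms are anticoagulated for at least 6 months. The bleeding comparison would therefore be incomplete even if stays were equal.

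That the windows differ, and that the comparison is distorted, is possible and even likely, but not established. If the CDT stay is longer, the effect would be to overstate the CDT excess, by an amount the protocol does not allow to be computed. This should be corrected. It does not touch the primary outcomes.

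**What to change.** - **Objective 3.2.1:** reword to clinically relevant bleeding, by the 7.4 definitions, from randomisation to the 6-month visit in each arm. Keep procedure-related bleeding as a descriptive subset within the CDT arm.
- **Visit 3 (6.5.3.1):** add bleeding since discharge to the history items in both arms, with the date of each event. Existing staff other than the assessor who scores PTS should ask. Section 6.5 keeps that assessor unaware of medical history and allocation, and an answer about a puncture-site bleed could reveal the arm.
- **Section 8.2:** report the proportion with clinically relevant bleeding per arm and the risk difference with its 95% confidence interval over that common window.

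The cost is one question at a visit that already takes place and three short text changes. There are two downsides: minor bleeds after discharge will rely on patient recall, and the question must be kept apart from the blinded PTS assessment. Asking at Visits 4 to 8 is not needed for this 6-month outcome.
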